Patients scheduled for an open or arthroscopic repair of a rotator cuff tear ≥ 2.5 cm will be identified during clinical visits or through EPIC. If the patient meets the eligibility inclusion/exclusion criteria for the study, he or she will be asked to participate in the study the following way:

During a patient's pre-operative clinical visit, the researcher will describe in detail the study at hand including, but not limited to, study benefits, potential risks, and alternative treatment modalities. He/she will hand a copy of the Informed Consent to the patient for review. If the patient agrees to participate in the study, the written informed consent will be completed and filed. The patient will be told explicitly that if he or she declines participation, his or her care will not be affected.

If patient is unavailable during pre-operative clinical visit, patient will be contacted via phone call. Any information regarding the study including IRB approved consent and brochure will be emailed and/or mailed to the patient for review. There will be documentation in the patient's chart when this patient was contacted via phone. Patient will be consented in-person on same-day as surgery, only if the above is completed and documented.

B. Enrolled Patients

After enrollment, all indicated preoperative assessments will be performed and recorded.

C. Randomization

All patients that meet the criteria will be randomized the day the informed consent is signed. If the patient is randomized into the control group, the surgery will continue as planned with no ECM scaffold graft to augment the repair. However, if the patient falls within the treatment group, an FDA-approved ECM scaffold graft will be used to augment the repair. The post-operative care will be as per standard care following a rotator cuff repair. There is no expectation that the patient should require a longer hospital stay.

D. Surgical Treatment

All surgical procedures will be performed by Board Certified and Fellowship trained Orthopedic Surgeons from Cleveland Clinic, [name] or as appointed by the PI. A standardized surgical repair technique will be used by the participating surgeon.

1. Control Treatment Group

Patients randomly assigned into the control group will undergo open or arthroscopic rotator cuff repair using the surgeon's standard practice. No ECM graft will be used.

2. Treatment Group

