Patients randomly assigned into the treatment group will undergo open or arthroscopic rotator cuff repair with A-FLEX graft to augment the repair. ECM scaffold grafts are indicated for the reinforcement of soft tissues repaired by sutures or suture anchors during tendon repair surgery, including rotator cuff.

3. Alternative Treatment Group

Patients who meet pre-op inclusion criteria where a repair cannot be accomplished due to intraoperative findings will remain in the study. This group will be analyzed separately and still follow study procedures.

E. Surgical Methods

Prior to repair

Tendon qualities and measurements will quantified and recorded:

- Tear size, retraction, quality of tissue

Arthroscopic Primary Rotator Cuff Repair

All patients will undergo arthroscopic primary repair using a suture bridge technique. An acromioplasty, distal clavicle excision and biceps tenodesis or tenotomy may be performed by routine techniques as clinically indicated. The tendon tear will be identified and mobilized, as indicated, such that the tendon can be approximated over the greater tuberosity. Standard double row suture bridge fixation technique will be used for all repairs

Mini-open/ Arthroscopic Graft Augmentation

In patients receiving a graft, thru mini open technique the lateral portal incision will be extended vertically approximately 5-6 cm. A standard, deltoid-splitting, mini-open approach will then be performed, leaving the deltoid attachment to the acromion intact. For arthroscopic technique same method of fixation will be used below. The dermis graft will be sized and cut so as to cover the entire repair site in both medial-lateral and anterior-posterior dimensions. The medial sutures previously placed in the tendon at the time of arthroscopic repair will then be passed in a mattress technique through the medial side of the graft. At least two

mattress sutures will be used, bringing the graft medial to the medial sutures used for the primary tendon repair. The graft will then be tensioned and secured in the anterior-posterior direction using at least two sutures on each side, passed through intact rotator cuff tissue. The suture limbs retained from the laterally placed suture bridge repair anchors will be placed as mattress sutures into the graft, and the graft will be tensioned to a position distal to the repair footprint.

Data for RCR will be recorded:

- Number of anchors
- Quality of repair
- Footprint coverage

3. Assessments

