Approximately 70 subjects are needed to assess the primary outcome, measured as the percentage of repairs that heal and remain intact after 1 year. A re-tear rate of 40% is expected in patients who have undergone rotator cuff repair for large and massive rotator cuff tears, based on the current literature (reference ted below). We anticipate that in this study, the percentage of re-tears in the augmented group will be reduced by

approximately half (~20%), while the control group would experience rates of re-tear comparable to what is reported in the current literature (~40%). Reducing this rate by half would be clinically meaningful. An SD of 15% within groups was allowed. Power analysis indicated that 20 patients in each group would provide sufficient power to identify statistical significance in healing rates between the control and augmented groups. With the assumption that the control group will have a failure rate of approximately 40% and the augmented group will have a failure rate of approximately 20%, at least 34 should be randomized in the control group and 26 in the augmented group. It is estimated that an overall fewer percentage of subjects initially randomized to the control group will complete the trial as augmentation may be required due to tear severity and other procedure variables. Those patients randomized to the control arm and withdrawn for repair by augmentation may be followed for safety.

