A power analysis was also considered for shoulder function, a secondary clinical outcome. It demonstrated that at least thirty-four cases must complete the study (seventeen cases in each arm- augmented and control) in order to assess the difference between each group. This sample size was statistically derived by an ASES score power analysis, using a power of 0.8, an effect size d of 0.9, an alpha error probability of 0.05, and an allocation ratio of 1. This is assuming an ASES score of 84 at 12 months postsurgical repair in the augmented group (standard deviation of 16) and 72 (standard deviation of 12) for the control group. The ASES data used was derived from a recently completed ArthroFlex rotator cuff repair study for which data is on file at LifeNet Health. Again, with the assumption that the control group will have a failure rate of approximately 40% and the augmented group will have a failure rate of approximately 20%, at least 30 should be randomized in the control group and 22 in the augmented group to assess a difference in shoulder function.

Once data is acquired for 15 subjects in each group, a post-hoc power analysis will be conducted to confirm that alpha and beta error probabilities are still under the accepted limits.

The primary analysis will be conducted on both the intent to treat and the per protocol populations. The intent to treat population will be comprised of all subjects that have completed rotator cuff repair surgery. The per protocol population will be comprised of all subjects that have completed all study visits and did not have any major protocol violations (e.g., missed visits, noncompliance with postsurgical instructions, etc.). Standard adjustments to analyses for pre-specified or baseline-suggested clinical covariates will be made; these covariate-adjusted analyses will be considered secondary analyses. Primary analysis results will be declared statistically significant if the two-sided p-value is less than 0.05.

Safety analyses will be performed on the intent to treat population and will include the incidence of treatment-emergent AEs and clinically significant changes in vital signs and

physical examinations. Impact of treatment on infection rate, treatment emergent AEs, and changes in vital signs and physical examination will all be assessed.

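### No analysis set contains all randomised patients, and the plan is inconsistent on whether controls who receive a graft are withdrawn or analysed

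*Combined protocol and SAP*

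**What the plan says.** **Timing.** Section 2C: "All patients that meet the criteria will be randomized the day the informed consent is signed". This precedes surgery even when consent is taken on the day of the operation. Section 6 (Labeling) describes the study as open-label.

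**Analysis sets.** Section 5 runs the primary analysis on two populations without ranking them. For the first: "The intent to treat population will be comprised of all subjects that have completed rotator cuff repair surgery". The second, per protocol, is limited to patients who attended every visit without a major violation. Safety uses the first set.

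**Unrepairable tears.** Section 2D, Alternative Treatment Group: patients "where a repair cannot be accomplished due to intraoperative findings will remain in the study", and "This group will be analyzed separately and still follow study procedures". The primary outcome in Section 5 is "measured as the percentage of repairs that heal and remain intact after 1 year".

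**Controls and the graft.** Section 2D, Control Treatment Group: "No ECM graft will be used". Section 5 nevertheless expects that fewer controls "will complete the trial as augmentation may be required due to tear severity and other procedure variables", and adds: "Those patients randomized to the control arm and withdrawn for repair by augmentation may be followed for safety".

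**The concern.** Randomisation protects the comparison only if the analysed groups are the randomised groups. Here membership of the main set depends on what happens in theatre, after allocation and with allocation known.

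There are two routes out of the set, and they differ in importance:

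- **Unrepairable tears** can occur in either arm. They unbalance the arms only if the judgement that a tear cannot be repaired differs by arm. They also leave the safety set, and the primary outcome is undefined for them because there is no repair to heal.
- **Augmented controls** can be lost only from the control arm, and the plan links that loss at least partly to tear severity. The Introduction names repair tension and tendon quality among the causes of failure. Withdrawing these patients can leave milder tears in the control arm and make the graft look worse than it is. A false claim of benefit becomes less likely, and a wrong finding of harm more likely.

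Section 5 makes covariate-adjusted analyses secondary. Adjusting for recorded tear size, retraction or tissue quality could not replace 1-year outcomes that were never collected for withdrawn controls.

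**Working it through.** **1. Who is in which set, taking the text literally**

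| Patient | "Intent to treat" (Section 5) | Other text |
|---|---|---|
| Randomised, repair completed as assigned | In | – |
| Randomised, no completed surgery | Out | – |
| Randomised, tear unrepairable | Out | Stays in the study; separate analysis (2D) |
| Control, graft used | In, because 2D describes the grafted operation as a rotator cuff repair; arm not stated | No graft in controls (2D); withdrawn, safety follow-up optional (5) |

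Per protocol is also conditional on events after randomisation. No set contains all randomised patients, and the last row has no single answer.

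**2. The plan's own allowance for loss**

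Section 5 starts from 20 per group and randomises at least 34 controls and 26 augmented patients. Using n/(1 − loss) with the assumed failure rates of 40% and 20% as the loss:

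- control: 20/0.60 = 33.3, rounded up to 34 (plan: 34)
- augmented: 20/0.80 = 25 (plan: 26)

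The stated numbers imply 14/34 = 41% of controls and 6/26 = 23% of augmented patients not evaluable. The plan therefore builds in unequal loss by arm. It does not say how much of that loss is augmentation.

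**3. Effect of withdrawing augmented controls when the graft does nothing**

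From the documents: 35 per arm, 40% control re-tear, two-sided 5% test. Assumed, because the documents give no figure: the proportion of controls withdrawn, w = 10–30%, and the re-tear risk of those withdrawn, r = 50–70%.

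Retained control risk = (0.40 − w·r)/(1 − w). For w = 20%, r = 60%: (0.40 − 0.12)/0.80 = 0.35.

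Rejection rates come from exact enumeration of the Pearson chi-square test, with graft n = 35 at 40% and the number of controls withdrawn Binomial(35, w).

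| w | r | Retained control risk | Total rejection | Against graft | For graft |
|---|---|---|---|---|---|
| 10% | 50% | 38.9% | 5.2% | 3.2% | 2.0% |
| 10% | 60% | 37.8% | 5.5% | 3.9% | 1.6% |
| 10% | 70% | 36.7% | 6.0% | 4.8% | 1.3% |
| 20% | 50% | 37.5% | 5.6% | 4.0% | 1.6% |
| 20% | 60% | 35.0% | 7.0% | 6.0% | 1.0% |
| 20% | 70% | 32.5% | 9.5% | 8.9% | 0.5% |
| 30% | 50% | 35.7% | 6.3% | 5.1% | 1.2% |
| 30% | 60% | 31.4% | 10.2% | 9.8% | 0.5% |
| 30% | 70% | 27.1% | 17.3% | 17.2% | 0.15% |

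Analysed as assigned, 35 v 35, the test rejects 4.8% of the time (2.4% each way). If withdrawn controls have average risk (r = 40%), the total is 5.1–5.2%.

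**4. If the graft halves re-tears, in augmented controls too**

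As-assigned difference = 0.20 − w·r/2. Withdrawal difference = retained control risk − 0.20.

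- w = 20%, r = 60%: 0.20 − 0.06 = 14.0 points as assigned; 0.35 − 0.20 = 15.0 points under withdrawal.
- w = 30%, r = 70%: 0.20 − 0.105 = 9.5 points as assigned; 0.271 − 0.20 = 7.1 points under withdrawal.

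The as-assigned difference is smaller in seven of the nine cells and larger in two (20%/70% and 30%/70%). Power at 20%/60% is 25.7% as assigned (34% v 20%), 28.0% under withdrawal (35% v 20%) and 45.3% with no crossover (40% v 20%).

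**The case against.** Several points on the other side have force.

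- **Section 2D against Section 5 on grafts in controls** can be read as a rule plus a foreseen departure from it. That reading is fair. It does not settle whether an augmented control is withdrawn or, having had a completed repair, is in the intent-to-treat set.
- **Unrepairable tears are partly handled.** They stay in follow-up, and a set limited to completed repairs suits an outcome defined on repairs. But that is a modified set, not intent to treat, and the plan offers no all-randomised analysis beside it.
- **The size is assumed throughout.** Six of the nine cells reject 7.0% of the time or less, and 17.3% is one corner. This stands, so the case rests on the definitions and not on the simulation.
- **The bias is conservative for a claim of benefit, and the remedy usually costs power.** At 20% withdrawn and 50% risk, power is 28.7% as assigned against 35.2% under withdrawal. This stands as a cost. It does not make a comparison of non-randomised groups valid, and a wrong finding of harm is also an error.
- **An all-randomised analysis needs a rule for missing 1-year MRI, and controls already withdrawn cannot be fully recovered.** Both are correct. The change summary cites large drop-out in a trial already under way. These points limit what the fix can achieve but do not remove the need for it.

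**Conclusion.** The concern holds and must be fixed. It follows from the text alone: the set labelled intent to treat is conditional on an event after randomisation, unrepairable tears are set aside, and Section 5 points both ways on augmented controls. The plan also names two populations for one primary test and does not say which governs, so with open-label data membership and arm could be decided after results are visible.

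The size is unknown. Under the withdrawal reading, and only if withdrawn controls are at above-average risk, the illustration gives total rejection of 5.2–17.3% with no graft effect, nearly all of the excess against the graft. At 20% withdrawn and 60% risk, false findings of harm rise from 2.4% to 6.0%, while false claims of benefit fall from 2.4% to 1.0%. There is no such bias if augmented controls are kept and analysed as assigned, and essentially none if those withdrawn have average risk.

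**What to change.** 1. Define intent to treat as all randomised patients, analysed in the arm to which they were assigned. Name this the single primary analysis and make per protocol a sensitivity analysis.
2. Reconcile Sections 2D and 5 so that any control who is augmented stays in the control arm for analysis and completes the scheduled ultrasound visits and 1-year MRI. Whether a control may be augmented is for the investigators to settle; nothing here takes a position on it.
3. State in advance how an unrepairable tear counts in the primary outcome within its assigned arm. Keep the separate analysis as supplementary.
4. State how a missing 1-year MRI is handled, since an all-randomised analysis depends on it.
5. Report augmentations, unrepairable tears and other exclusions by arm.

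**Cost.** Protocol wording, plus completion of visits and imaging already in the schedule. Missed assessments in any control already withdrawn may be unrecoverable and should be reported as such. Crossover dilutes the contrast: in the 20%/60% illustration, power is about 26% as assigned, against about 28% under withdrawal and 45% with no crossover. The gain is a valid randomised comparison, not a larger effect or more power.

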Introduction

Despite advances in surgical technology, repairs of large (3-5 cm) and massive (>5 cm) rotator cuff tears (RCT) fail from 20-90% [1]. Due to their size and increased structural involvement, large or massive RCT present a substantial challenge to orthopaedic surgeons. [16] The repairs tend to fail at the suture-tendon junction, which is due to several factors, including tension at the repair and quality of the tendon [1-2,5]. Full thickness tears are uncommon in younger patients, especially those less than forty years old and are usually traumatic in etiology. Younger patients also typically fair better following arthroscopic rotator cuff repair with fewer failures and more successful return to pre-injury level of function [16]. One strategy to augment repair of large to massive rotator cuff tears has been the development of biological scaffold materials, which are composed of extracellular matrix (ECM). The ECM composing the scaffolds are made from a number of tissues, including, but not limited to, small intestinal submucosa (SIS), dermis, and pericardium [3]. Studies to date include both prospective and retrospective in animal and human models, and include Restore, a porcine-derived SIS by DePuy Orthopaedics, GraftJacket, a human-derived, non-cross-linked dermis graft by Wright Medical Technology, and Zimmer Collagen Repair, a cross-linked porcine derived dermal graft made by Zimmer. Restore studies have shown no benefit and some even an increase in repair failure with recommendations not to use to augment repair [1, 4-8]. GraftJacket studies have shown a reduction in graft failure [1, 9-11]; however, several of the Restore and GraftJacket studies are limited by a lack of a control cohort. The Zimmer graft studies have conflicting results with both an improvement and no improvement in failure rates of repair [1,12,13]. The prior studies listed are all *in vivo*; however, the majority are not randomized trials and thus do not have a control with which to compare data. In addition, some trials include open repairs. A lack of prospective, randomized, controlled, *in vivo* trials exist that evaluate the ability of the ECM scaffold graft augmentation in large to massive arthroscopic rotator cuff repairs to decrease the failure rate.

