The purpose of this study is to evaluate the efficacy of using the Arthroflex (A-FLEX) graft to augment large to massive arthroscopic rotator cuff repairs *in vivo* and decrease repair failures in a prospective, randomized, controlled trial. By undergoing serial US examinations at follow-ups, we also intend to evaluate when during the postoperative period the failure of the repair occurs.

1. Study Design

Methods

This is a prospective, randomized, controlled, multi-center clinical trial to evaluate the effectiveness of an ECM scaffold graft to augment repair of a large/massive rotator cuff tear. The study will involve 70 patients. 35 patients will be randomly assigned to each arm of the study.

A-FLEX graft will be used in those patients randomly assigned to the treatment group who are undergoing an arthroscopic large (defined as 2.5-5 cm) or massive (defined as >5 cm) rotator cuff repair. Patients randomly assigned into the control group will undergo open or arthroscopic rotator cuff repair using the surgeon's standard technique.

A. Inclusion Criteria

The following patients will be found eligible for inclusion into the study sample:

1. Patients with a large (2.5-5 cm) to massive (>5 cm) rotator cuff tear who will be undergoing open or arthroscopic repair. The cuff tear size will be determined on either pre-operative magnetic resonance imaging (MRI), or ultrasound (US), or intra-operative measurements, or computerized tomography (CT).
2. Patients who are willing and able to provide written informed consent for their involvement in the study.
3. Patients who meet criteria for RCR surgery.
4. Patients older than 18 years of age.

B. Exclusion Criteria

The following patients will not be found eligible for inclusion into the study sample.

1. Those with a known sensitivity to materials of porcine origin.
2. Patients with addiction to illegal drugs, solvents or alcohol who are actively using or have previously attempted and failed a treatment program.
3. Patients with bacteremia, a systemic infection, or infection of the surgical site.
4. All those who are prisoners.
5. Patients who are pregnant or nursing.
6. All those with a condition that may limit a patient's ability to finalize the study or that may cause an undue risk to the patient's health and well-being.

2. Research Procedures

Treatment Plan

A. Preoperative Screening

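### Tear size has no place in the primary comparison and adjustment covariates may be chosen from baseline data; fixing pre-allocation tear-size class as a primary-analysis factor is a cheap improvement

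*Combined protocol and SAP*

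**What the plan says.** Section 5 (Sample Size Justification and Statistical Analysis) deals with covariates in one sentence: "Standard adjustments to analyses for pre-specified or baseline-suggested clinical covariates will be made; these covariate-adjusted analyses will be considered secondary analyses". It names no covariate and no primary test. The next sentence sets the decision rule: "Primary analysis results will be declared statistically significant if the two-sided p-value is less than 0.05".

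Section 1.A admits "Patients with a large (2.5-5 cm) to massive (>5 cm) rotator cuff tear" and lets size come from preoperative MRI, ultrasound, CT or intra-operative measurement. Section 2.C says "All patients that meet the criteria will be randomized the day the informed consent is signed" and gives no stratification factor, block size or method. Tear size is recorded before the repair (Section 2.E) and again under Operative Assessments (Section 3.B). The preoperative list in Section 3.A mentions shoulder imaging but not a size. Section 6 calls the study open-label.

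The planning assumption in Section 5 is one rate for both classes: "A re-tear rate of 40% is expected in patients who have undergone rotator cuff repair for large and massive rotator cuff tears". The Introduction says "Due to their size and increased structural involvement, large or massive RCT present a substantial challenge", and quotes failure of 20-90% for large and massive tears together.

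**The concern.** Tear size defines the population and is measured, yet no analysis uses it. If massive tears re-tear more often than large ones, a chance excess of massive tears in one arm moves the primary contrast directly, and with 35 per arm such an excess is not rare. Stratified analysis on a factor fixed in advance removes most of that dependence.

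The wording on covariates adds a second, smaller problem. A covariate suggested by baseline data is one chosen after the data are seen. Because no list exists, a reader cannot tell which adjusted result was planned, and the analysts of an open-label trial may know the allocation when they choose.

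**Working it through.** **The plan's own figure.** The plan gives no figure for adjustment. Its sample size rests on 40% versus 20% re-tear and 20 evaluable patients per group. For two proportions at two-sided 0.05 and 80% power, n = [1.96√(2·0.3·0.7) + 0.842√(0.4·0.6 + 0.2·0.8)]² / 0.2² = (1.270 + 0.532)² / 0.04, which gives 82 per arm, so 20 is not reproduced. Power is 28% at 20 per arm and 44.5% at 35. That is a separate defect and adjustment does not repair it.

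**Inputs.** From the documents: 35 per arm, control re-tear 40%, augmented 20%, alpha 0.05 two-sided. Assumed, because the documents give neither: 20%, 30% or 50% massive tears, and large/massive re-tear rates of 30/50%, 25/55% or 20/60% (gaps of 20, 30 and 40 points; these average 40% when half the tears are massive).

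**Step 1: how often imbalance occurs.** Take two independent Binomial(35, m) counts of massive tears. The SD of the difference in share is √(2m(1−m)/35): 9.6 points at m = 0.2 and 12.0 at m = 0.5. The exact probability of a difference of 20 points or more (7 or more patients) is 5.1%, 8.9% and 12.0% at m = 0.2, 0.3 and 0.5. A difference of 10 points or more occurs in 36-40% of trials at m = 0.3-0.5.

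**Step 2: how far it moves the result.** Shift = imbalance × gap. For 20 points this is 0.2 × 20, 30 or 40 = 4, 6 or 8 points, or 1.4 to 2.8 patients out of 35. One patient can decide the verdict: 14/35 versus 7/35 gives p = 0.068 and 14/35 versus 6/35 gives p = 0.034 (uncorrected chi-square).

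**Step 3: false positives by hand.** With 40% in both arms the standard error is √(2·0.4·0.6/35) = 11.7 points, so the shifts are 0.34, 0.51 and 0.68 standard errors. The chance that |Z + shift| exceeds 1.96 is about 6.3%, 8.1% and 10.5%.

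**Step 4: simulation.** 600,000 trials per scenario; unadjusted pooled z test against Mantel-Haenszel stratified on size; no graft effect, listed rates in both arms. Entries are % significant.

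| Massive share | Large/massive re-tear | Unadjusted, all trials | Unadjusted, imbalance ≥20 points | Stratified, imbalance ≥20 points | Either test, all trials |
|---|---|---|---|---|---|
| 20% | 30/50% | 5.2 | 6.7 | 5.0 | 5.9 |
| 20% | 20/60% | 4.9 | 11.5 | 5.1 | 6.5 |
| 30% | 20/60% | 5.1 | 11.7 | 4.8 | 6.8 |
| 50% | 30/50% | 4.8 | 6.2 | 5.0 | 5.8 |
| 50% | 25/55% | 4.9 | 8.1 | 5.0 | 6.3 |
| 50% | 20/60% | 4.9 | 10.5 | 5.0 | 6.8 |

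With all rates multiplied by 0.75 (mean 30% when half are massive), the conditional unadjusted rate is 5.7-9.1% and the overall rate 4.8-5.1%. If the rates are instead re-centred to a 40% mean at every massive share, the highest conditional rate is 10.4%.

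**Step 5: power.** If the graft halves risk in each class and half the tears are massive, power goes from 45.4% to 45.5%, 45.4% to 46.9% and 45.3% to 48.9% for gaps of 20, 30 and 40 points. In the same scenarios, when control has at least 15 points more massive tears, the unadjusted chance of a significant benefit is 57-69%; when the graft arm has them it is 34-23%. Stratified, it is 44-48% either way. If the same absolute gap holds in both arms, the gain reaches 7 points (45.3% to 52.7%), but the 40-point gap then requires graft rates of 0% and 40%.

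**The case against.** The strongest reply is that randomisation already pays for chance imbalance. Over all trials the unadjusted test holds 4.8-5.2% in these simulations, so a reader who infers an invalid or inflated primary test would be wrong; the 6-12% applies only to the minority of trials with a large imbalance. This stands. An unadjusted primary analysis with adjusted secondary ones is a legitimate design.

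Second, a reader might infer that the primary verdict can be picked from several adjusted results. The text does not support that: adjusted analyses are labelled secondary, and the 0.05 rule is applied to primary results. The 5.5-7% figure describes what would happen if that boundary were not kept.

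Third, a reader might infer that the documents show massive tears failing more often than large ones. They do not. The Introduction blames tension and tendon quality, speaks of large and massive tears together, and does not split its 20-90% range. The gap and the massive share are therefore assumptions; at 10% massive, a 20-point imbalance occurs in only about 1% of trials.

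Fourth, that the primary test is unadjusted and the randomisation unstratified is inferred: the first from the secondary label, the second from silence.

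Fifth, the size the protocol explicitly records is an operative value, taken after allocation in an open-label trial. A uniform pre-allocation size is not assured for every patient. This also stands and shapes the fix.

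None of this removes the case for fixing one obvious factor and a closed covariate list in advance.

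**Conclusion.** The point holds as a low-cost improvement, not as an error that invalidates the primary test. What the plan leaves open is dependence on the imbalance that happens to occur: about 5-12% of trials would have a difference of 20 points or more, with a conditional false-positive rate of about 6-12% against about 5% stratified. The overall power gain is about 0-4 points under proportional benefit, and power stays below 50% in those scenarios. These sizes rest on an assumed 20-50% share of massive tears and an assumed re-tear gap of 20-40 points; if the gap is near zero, so is the benefit. The open-ended covariate wording is a flaw in the secondary analyses only.

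**What to change.** Before outcomes are analysed, amend Section 5 to:

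- Name the primary test and make tear-size class (2.5-5 cm versus >5 cm) a pre-specified factor in it: a Mantel-Haenszel risk difference and test, or logistic regression with a standardised risk difference.
- Take the class from the size determined for eligibility before allocation, not from the operative record, and use one definition; the Introduction still gives 3-5 cm for large.
- State in advance how patients sized only in surgery are handled, for example as a separate stratum of those not sized before allocation.
- Report the unadjusted result as a sensitivity analysis.
- Remove the baseline-suggested option and list any further covariates.

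The cost is SAP wording, plus abstraction of one pre-allocation size per patient from preoperative imaging, which may be missing or measured by different methods for some. No added patients are needed. Stratifying the randomisation on the same two classes is optional: the summary of changes cites drop-outs and screen failures, so enrolment has begun and stratification can help only patients still to be randomised.
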